13.2 Informed consent

The investigator must explain to each subject (or legally authorized representative) the nature of the study, its purpose, the procedures involved, the expected duration, the potential risks and benefits involved and any discomfort it may entail. Each subject must be informed that participation in the study is voluntary and that he/she may withdraw from the study at any time and that withdrawal of consent will not affect his/her subsequent medical treatment or relationship with the treating physician.

This informed consent should be given by means of a standard written statement, written in non-technical language. The subject should read and consider the statement before signing and dating it, and should be given a copy of the signed document. If the subject cannot read or sign the documents, oral presentation may be made or signature given by the subject's legally appointed representative, if witnessed by a person not involved in the study, mentioning that the patient could not read or sign the documents. No patient can enter the study before his/her informed consent has been obtained.

The informed consent form is considered to be part of the protocol, and must be submitted by the investigator with it for IRB approval. The original signed copy of the consent document must be retained in the medical record or research file.

13.3 Committees

13.3.1 Scientific Review Committee (SRC)

Each SRC conducts a formal internal peer review of all clinical protocols and general scientific oversight of interventional clinical research. Protocols are reviewed for scientific merit, adequate study design, safety, availability of targeted study population, and feasibility of timely completion of all proposed research projects to be conducted by its assigned programs at the Cancer Center. Each SRC is responsible for evaluation the risk/benefit assessment and corresponding data and safety monitoring plan as part of the scientific review and approval process.

13.3.2 Data Safety Monitoring Committee (DSMC)

The DSMC will meet on a monthly basis and will continually assess for subject safety and recommend changes to protocol and study as required to preserve subject safety and prevent any untoward toxicity.

13.3.3 Protocol monitoring Committee (PMC)

This study will be reviewed by the PMC for data and safety monitoring. The PMC monitors its assigned ongoing research protocol for: adverse event reporting, data and safety monitoring, and internal audit findings. The PMC, upon review of any agenda item, may approve the study for continuation, require revisions, suspend or close a protocol.

13.4 Internal monitoring

The trial will be monitored per Moffitt Cancer Center policy MRI-P.PSO.03, *Monitoring of Investigator Initiated Clinical Research*. Data will be captured in Oncore, Moffitt's Clinical Trials Database, Regulatory documents and case report forms will be monitored internally according to Moffitt Cancer Center Monitoring Policies. Monitoring will be performed regularly to verify data is accurate, complete and verifiable from source documents; and the conduct of the trial is in compliance with the currently approved protocol/amendments, Good Clinical Practice, and applicable regulatory requirements.

13.5 Ethics and Good Clinical Practice (GCP)

It is the responsibility of the investigator to have prospective approval of the trial protocol, protocol amendments, informed consent forms, and other relevant documents, e.g., advertisements, if applicable, from the IRB/IEC. The trial will be performed in accordance with the protocol, International Conference on Harmonization Good Clinical Practice guidelines, and applicable local regulatory requirements and laws.

It is understood that deviations from the protocol should be avoided, except when necessary to eliminate an immediate hazard to a research participant. In such case, the deviation must be reported to the IRB according to the local reporting policy.

13.6 Declaration of Helsinki

The investigator must conduct the trial in accordance with the principles of the Declaration of Helsinki. Copies of the Declaration of Helsinki and amendments will be provided upon request

or can be accessed via the website of the World Medical Association at http://www.wma.net/e/policy/17-c_e.html.

13.7 Study documentation

The investigator must prepare and maintain adequate and accurate case histories designed to record all observations and other data pertinent to the study for each research participant. This information enables the study to be fully documented and the study data to be subsequently verified.

Original source documents supporting entries in the case report forms include but are not limited to hospital records, clinical charts, laboratory and pharmacy records, recorded data from automated instruments, microfiches, photographic negatives, microfilm or magnetic media, and/or x-rays.

APPENDIX A:

Inhibitors of CYP3A are defined as follows. A comprehensive list of inhibitors can be found at the following website: <http://medicine.iupui.edu/clinpharm/ddis/table.aspx>. The general categorization into strong, moderate, and weak inhibitors according to the website is displayed below. Refer to Section 5.2 on instructions for concomitant use of CYP3A inhibitors and inducers with ibrutinib.

Inhibitors of CYP3A	Inducers of CYP3A
Strong inhibitors:	
INDINAVIR	Carbamazepine
NELFINAVIR	Efavirenz
RITONAVIR	Nevirapine
CLARITHROMYCIN	Barbiturates
ITRACONAZOLE	Glucocorticoids
KETOCONAZOLE	Modafinil
NEFAZODONE	Oxcarbazepine
SAQUINAVIR	Phenobarbital
SUBOXONE	Phenytoin
TELITHROMYCIN	Pioglitazone
Moderate inhibitors:	Rifabutin
Aprepitant	Rifampin
Erythromycin	St. John's Wort
diltiazem	Troglitazone
Fluconazole	
grapefruit juice	
Seville orange juice	
Verapamil	
Weak inhibitors:	
Cimetidine	
All other inhibitors:	
Amiodarone	
NOT azithromycin	
Chloramphenicol	
Boceprevir	
Ciprofloxacin	
Delavirdine	
diethyl-dithiocarbamate	
Fluvoxamine	
Gestodene	
Imatinib	
Mibepradil	
Mifepristone	
Norfloxacin	
Norfluoxetine	
star fruit	
Telaprevir	
Troleandomycin	
Voriconazole	

Source: <http://medicine.iupui.edu/clinpharm/ddis/table.aspx>.

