4.4.2 Exclusion criteria

1. High grade NET or small cell neuroendocrine carcinoma;
2. Clinically apparent central nervous system metastases or carcinomatous meningitis;
3. Known positive test for human immunodeficiency virus (HIV), hepatitis B virus (HBV), or hepatitis C virus (HCV);
4. History of stroke or intracranial hemorrhage within 6 months prior to the first dose of study drug;
5. Clinically significant cardiovascular disease such as uncontrolled or symptomatic arrhythmias, congestive heart failure, or myocardial infarction within 6 months of screening, or any class III or IV cardiac disease as defined by the NYHA functional classification;
6. Requirement for anticoagulation with warfarin or similar vitamin K antagonists.

7. Requirement for treatment with a strong cytochrome P450 (CYP) 3A4/5 inhibitor. (See Appendix A)
8. Prior antitumor therapy within 2 weeks of enrollment (with the exception of somatostatin analogs);
9. No other active malignancy within 3 years of enrolment except adequately treated basal cell or squamous cell skin cancer, in situ cervical cancer, adequately treated stage I or II cancer from which the patient is currently in complete remission, or any other cancer from which the patient has been disease free for at least three years;
10. Any medical condition or organ system dysfunction which, in the investigator's opinion, could compromise the patient's safety, interfere with the absorption or metabolism of ibrutinib;
11. Known hypersensitivity to ibrutinib or any component of the ibrutinib formulation;
12. History of noncompliance to medical regimens or unwillingness to comply with the protocol.
13. Currently active, clinically significant hepatic impairment Child-Pugh class B or C according to the Child Pugh classification (see Appendix D)

Comment [AT2]: RESPONSE REQUIRED:

Please include the following exclusion criteria regarding hepatotoxicity.

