5.1 Study drug: ibrutinib

The investigational drug used in this study is ibrutinib, available as 140 mg capsules. The inactive ingredients of ibrutinib include: microcrystalline cellulose, croscarmellose sodium, sodium lauryl sulfate and magnesium stearate.

Pharmacyclics will supply ibrutinib as long as the patient remains on study, shows continuous benefit from treatment, and there are no safety concerns. Ibrutinib should be stored at room temperature (20°C to 25°C, equivalent to 68°F to 77°F). Excursions are permitted between 15°C and 30°C (59°F to 86°F).

The starting dose is 560 mg (four 140 mg capsules) taken once daily orally. Doses should be taken approximately the same time each day, without scheduled breaks. Patients who vomit anytime after taking a dose should not “make it up” with extra doses, but instead resume subsequent doses as planned. Any missed dose may be taken as soon as possible on the same day with a return to the normal schedule the following day. If doses are missed or vomited, this must be indicated in the source documents and CRFs. A treatment cycle will be defined as 4 weeks duration. To monitor the correct self-administration of ibrutinib, enrolled patients will be provided with a diary.

Study treatment should begin within 14 days following enrollment onto the study. Patients should be requested to bring their unused medication to the clinic each visit. Compliance should be verified by the investigator's staff through counting the number of capsules consumed between visits. The investigator (or his/her designee) will document dosage administration and all dose changes during the study in the CRF. The dose, amount dispensed, amount received, and amount remaining unused must be recorded.

Patients will be assessed for response after every 3 cycles (12 weeks) of therapy. Patients with evidence of stable disease or response to therapy as defined by RECIST v1.1 will continue protocol therapy. The dose of ibrutinib will be adjusted for toxicity as outlined below. Patients with unacceptable toxicity or progressive disease will discontinue protocol therapy.

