5.2 Dose Modification

Ibrutinib should be held or reduced in dose for toxicity or for concomitant use of CYP3A inhibitors (see Appendix A), as described in the sections below. Ibrutinib dosing adjustments are to be made according to the greatest degree of toxicity observed. Doses of ibrutinib which have been reduced for toxicity may not be re-escalated. All interruptions or changes to study drug administration must be recorded. If any patient discontinues study treatment or post-treatment observation, then the reason will be recorded.

Patients experiencing drug-related toxicities that are grade 1 or 2 according to CTCAE criteria should continue ibrutinib without dose modification. However the investigator may reduce the dose by one level if a grade 2 toxicity persists and significantly affects patient quality of life. If a patient experiences a CTCAE grade 3 or higher non-hematological toxicity, a grade 3 or higher neutropenia with infection or fever, or a grade 4 hematological event that is considered drug-related, ibrutinib should be held until resolution of toxicity to ≤ grade 1. Then the drug should be reinitiated at the starting dose. If the toxicity reoccurs, the dose should be reduced by one capsule (140 mg per day). A second reduction of dose by 140 mg may be considered as needed as per Table 5-2. If a patient experiences these drug-related toxicities despite two dose reductions, ibrutinib should be discontinued and the patient should be taken off the study. Patients should also be removed from study if off treatment for >3 weeks.

Recommended dose modifications for these toxicities are described below:

Table 5-2: Recommended dose modifications for ibrutinib

Toxicity occurrence	Dispensed As
First	Restart at 560 mg daily
Second	Restart at 420 mg daily
Third	Restart at 280 mg daily
Fourth	Discontinue Ibrutinib

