5.3 Concomitant therapy

- All patients should be maintained on the same medications throughout the study period, as medically feasible;
- The investigator should instruct the patient to notify the study staff about any new medications he/she takes after the start of the study drug. All medications (other than study drug) and significant non-drug therapies (including physical therapy and blood transfusions) administered after the patient starts treatment with study drug must be recorded;
- Administration of pegfilgrastim or filgrastim following initiation of protocol therapy is at investigator's discretion for all patients;
- Administration of erythropoietin or darbopoietin is allowed;
- Other concurrent investigational drugs of any type are not allowed in the trial;
- Other concurrent anticancer agents (with the exception of somatostatin analogs) are not allowed in the trial;
- Patients must be instructed not to take any additional medications (including herbal supplements and over-the-counter products) during the trial without prior consultation with the investigator. All medications taken within 30 days of screening should be recorded. If concomitant therapy must be added or changed, the reason and name of the drug/therapy should be recorded;
- In general, the use of any concomitant medication/therapies deemed necessary for the care of the patient are allowed, including drugs given prophylactically (e.g. antiemetics or steroids), with the following exceptions:
- CYP3A Inhibitors/Inducers
 - Ibrutinib is metabolized primarily by CYP3A. Avoid co-administration with strong or moderate CYP3A inhibitors and consider alternative agents with less CYP3A inhibition.

- Strong inhibitors of CYP3A (eg, ketoconazole, indinavir, nelfinavir, ritonavir, saquinavir, clarithromycin, telithromycin, itraconazole, nefazadone, or cobicitstat) should be avoided
- If a strong CYP3A inhibitor (see Appendix A) must be used, ibrutinib will be reduced to 140 mg or withheld for the duration of inhibitor use.. Subjects will be monitored more closely for signs of ibrutinib toxicity (at the investigator's discretion). If a moderate CYP3A inhibitor (see Appendix A) must be used, ibrutinib will be reduced to 140 mg (for 840 mg/day dose, reduce to 280mg) for the duration of the inhibitor use. No dose adjustment is required in combination with mild inhibitors.

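### Section 5.3 sets the ibrutinib dose by three CYP3A inhibitor classes, but Appendix A puts 17 of its 35 listed inhibitors in a fourth group that no section covers

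*Combined protocol and SAP*

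**What the plan says.** The relevant text is spread over four places in the protocol.

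- **Section 5.2 (Dose Modification)** makes a general statement, "Ibrutinib should be held or reduced in dose for toxicity or for concomitant use of CYP3A inhibitors (see Appendix A"), and the same sentence then defers to the sections that follow it for the details. It gives no dose for inhibitor use.
- **Section 5.3 (Concomitant therapy)** holds the class rules. Strong: "If a strong CYP3A inhibitor (see Appendix A) must be used, ibrutinib will be reduced to 140 mg or withheld". Moderate: "If a moderate CYP3A inhibitor (see Appendix A) must be used, ibrutinib will be reduced to 140 mg", with an added clause for patients on 840 mg/day. Mild: "No dose adjustment is required in combination with mild inhibitors". The advice to avoid co-administration names strong and moderate inhibitors only. The section also names ten strong inhibitors as examples, and it refers sites to a website that it says is continually revised.
- **Appendix A** says of its own contents: "The general categorization into strong, moderate, and weak inhibitors according to the website is displayed below". The table has strong, moderate and weak headings and then "All other inhibitors". It sends readers to Section 5.2 for instructions on concomitant use.
- **Section 4.4.2, exclusion criterion 7**, excludes patients with this need: "Requirement for treatment with a strong cytochrome P450 (CYP) 3A4/5 inhibitor. (See Appendix A").

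Section 5.1 fixes the dose from which any reduction starts: "The starting dose is 560 mg (four 140 mg capsules) taken once daily orally".

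**The concern.** A dose rule keyed to drug class works only if the classification covers every drug on the list. Here a drug can appear in the protocol's own table of CYP3A inhibitors and still have no class on which Section 5.3 can act. The investigator must then choose. Treating the drug as mild leaves the dose unchanged, treating it as moderate takes it to 140 mg, and treating it as strong takes it to 140 mg or stops it for the duration of inhibitor use. Section 13.1 refers to participating investigators in the plural, so the choice need not be the same for every patient.

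Three things are at stake.

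- **Safety.** A patient could stay at full dose while taking a drug that the protocol lists as an inhibitor. Section 1.3.2.1 reports significant pharmacokinetic interactions with a strong CYP3A4/5 inhibitor.
- **Consistency of treatment.** Section 5.2 removes patients who are off treatment for more than 3 weeks, so a decision to withhold could also determine whether a patient stays on study.
- **Eligibility.** Criterion 7 uses the same list, so a drug with no class, or one missing from the list, may be screened differently from patient to patient.

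**Working it through.** The plan states no total to reproduce, so the check is a count, a trace of the rules and a dose ratio.

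**1. Count of Appendix A (inhibitor column).** Strong 10, moderate 7, weak 1. The fourth group has 18 lines, one of which says that azithromycin is not an inhibitor, leaving 18 − 1 = 17.

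- Total: 10 + 7 + 1 + 17 = 35.
- Share in the fourth group: 17 / 35 = 48.6%.
- If imatinib is taken to be an anticancer agent (an assumption; the documents do not label it), Section 5.3 already bars it. The figure becomes 16 of 34 = 47.1%.

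**2. Trace of the rule for each group.**

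| Appendix A heading | Entries | Matching class in 5.3 | Rule in 5.3 |
|---|---|---|---|
| Strong | 10 | Strong | 140 mg or withheld |
| Moderate | 7 | Moderate | 140 mg |
| Weak | 1 | Mild, if the two words mean the same | No adjustment |
| All other | 17 | None | None |

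Following the cross-references does not fill the last row. Appendix A points to Section 5.2, which points back to Appendix A and on to later sections. Those later sections cover strong, moderate and mild only.

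**3. Size of the possible difference.** Ratio = current dose / 140 mg, using the starting dose from Section 5.1 and the reduced doses from Table 5-2.

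- At 560 mg: 560 / 140 = 4.0
- At 420 mg: 420 / 140 = 3.0
- At 280 mg: 280 / 140 = 2.0

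If a site reads the drug as strong and withholds, the contrast is the current dose against none.

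**4. Comparison of the strong lists.** Section 5.3 names ten drugs. Nine are under the strong heading in Appendix A, allowing for a spelling difference in nefazodone. The tenth, cobicistat (misspelled in 5.3), appears nowhere in Appendix A. In the other direction, Suboxone is strong in Appendix A and is not named in 5.3.

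**5. A dose that this trial does not use.** The moderate rule in 5.3 carries a clause for 840 mg/day. The starting dose is 560 mg and Table 5-2 only goes down from there.

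**The case against.** Several arguments against the point have force.

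- **Section 5.2 is not a rival rule.** A reader might infer that 5.2 says to reduce while 5.3 says nothing, so that the two conflict. The documents do not support that. The sentence in 5.2 defers to later sections and gives no inhibitor dose. The fault is an uncovered group, and the 140 mg figure arises only if a site itself classes the drug as moderate or strong.
- **The website may classify these drugs.** Section 5.3 sends sites there, to a different page from the one that Appendix A cites. A reader might infer that it cannot help because it is also the source of the Appendix A grouping. Its content cannot be judged from the documents. What stands is narrower: the protocol does not say that the website decides the class, and it describes the site as changing over time.
- **The strong list in 5.3 is only examples, and 5.3 calls Appendix A a list of common drugs.** Neither claims to be complete, and criterion 7 is worded by class. Cobicistat would therefore still fall under the strong rule on study. Even so, a drug that the protocol itself names as strong should be in the list used for screening.
- **Safeguards exist.** Patients must consult the investigator before taking additional medication, concomitant medications are documented at each visit, and dose changes and interruptions are recorded. A reader might infer that toxicities could not be related to the dose received; these records argue against that. They do not tell the investigator what to do.
- **Some entries are unlikely to arise.** Concurrent anticancer agents are barred, and known HIV and HCV infection are exclusions. This limits the practical reach by an amount that the documents do not let one estimate.

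**Conclusion.** The point holds as an internal inconsistency. Appendix A announces three classes and prints four, Section 5.3 acts on three, and 17 of 35 listed inhibitors have neither a class nor a dose rule. The mismatched class names (weak against mild), the pointer to the wrong section and the missing cobicistat entry add to it, and criterion 7 carries the problem into eligibility.

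The size needs careful reading. The 48.6% is a share of list entries. A reader might infer that about half of co-medicated patients, or of exposures, are affected, but the documents give no frequency of use. The fourfold gap applies only at 560 mg and shrinks after dose reduction. No effect on the response rate or on the two-stage decision rules can be calculated.

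The conclusion rests on the text of Sections 4.4.2, 5.2 and 5.3 and Appendix A, and on the assumption that weak and mild mean the same class. If they do not, the single weak entry also lacks a rule. The point should be corrected because it concerns patient safety and is cheap to put right; it does not undermine the primary analysis.

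**What to change.** Reconcile Appendix A, Sections 5.2 and 5.3 and exclusion criterion 7 so that:

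- every inhibitor listed in Appendix A is covered by a stated rule, whether by giving the fourth group's drugs a class or by stating a rule for the group;
- the strong inhibitors named in Section 5.3 and Appendix A agree, so that criterion 7 screens on the same list;
- one term is used for the lowest class, and Appendix A points to the section that holds the class rules;
- the protocol says what standing the website has when a drug's class is in doubt;
- the 840 mg/day clause in Section 5.3 is reconciled with the 560 mg starting dose.

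Which class each drug belongs to, and what rule applies, are for the sponsor and the drug supplier to decide; this review proposes neither.

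The cost is an edit to one appendix table and matching text in the sections named, handled as a protocol amendment. The downside is that some patients may have their dose handled differently, or be screened out, once the list is complete.

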Appendix B: EORTC QLQ-C30 (version 3)

EORTC QLQ-C30 (version 3)

We are interested in some things about you and your health. Please answer all of the questions yourself by circling the number that best applies to you. There are no "right" or "wrong" answers. The information that you provide will remain strictly confidential.

Please fill in your initials:

Your birthdate (Day, Month, Year):
Today's date (Day, Month, Year):

31

	Not at All	A Little	Quite a Bit	Very Much
1. Do you have any trouble doing strenuous activities, like carrying a heavy shopping bag or a suitcase?	1	2	3	4
2. Do you have any trouble taking a long walk?	1	2	3	4
3. Do you have any trouble taking a short walk outside of the house?	1	2	3	4
4. Do you need to stay in bed or a chair during the day?	1	2	3	4
5. Do you need help with eating, dressing, washing yourself or using the toilet?	1	2	3	4

During the past week:

	Not at All	A Little	Quite a Bit	Very Much
6. Were you limited in doing either your work or other daily activities?	1	2	3	4
7. Were you limited in pursuing your hobbies or other leisure time activities?	1	2	3	4
8. Were you short of breath?	1	2	3	4
9. Have you had pain?	1	2	3	4
10. Did you need to rest?	1	2	3	4
11. Have you had trouble sleeping?	1	2	3	4
12. Have you felt weak?	1	2	3	4
13. Have you lacked appetite?	1	2	3	4
14. Have you felt nauseated?	1	2	3	4
15. Have you vomited?	1	2	3	4
16. Have you been constipated?	1	2	3	4

Please go on to the next page.

During the past week:

	Not at All	A Little	Quite a Bit	Very Much
17. Have you had diarrhea?	1	2	3	4
18. Were you tired?	1	2	3	4
19. Did pain interfere with your daily activities?	1	2	3	4
20. Have you had difficulty in concentrating on things, like reading a newspaper or watching television?	1	2	3	4
21. Did you feel tense?	1	2	3	4
22. Did you worry?	1	2	3	4
23. Did you feel irritable?	1	2	3	4
24. Did you feel depressed?	1	2	3	4
25. Have you had difficulty remembering things?	1	2	3	4
26. Has your physical condition or medical treatment interfered with your family life?	1	2	3	4
27. Has your physical condition or medical treatment interfered with your social activities?	1	2	3	4
28. Has your physical condition or medical treatment caused you financial difficulties?	1	2	3	4

For the following questions please circle the number between 1 and 7 that best applies to you

29. How would you rate your overall health during the past week?

1 2 3 4 5 6 7

Very poor

Excellent

30. How would you rate your overall quality of life during the past week?

1 2 3 4 5 6 7

Very poor

Excellent

